#### 4.3.2 Post-Dosing Efficacy Observations

While double blind treatment period efficacy observations will be listed regardless of whether the patient was taking blinded study drug. Observations will be included in summarizes of the FAS only if the following rules are satisfied:

- HbA1c, body weight, BMI and CCI will be summarized only if measured on or before the 8th day after the last double-blind drug dosing date.
- FPG, CCI SBP, eGFR and Insulin initiation will be summarized only if measured on or before the 1st day after the last randomized, double-blind drug dose date.
- Lipids and other exploratory parameters (if available) will be summarized only if measured on or before the 4th day after the last randomized, double-blind drug dose date.
- The efficacy measurements of HbA1c and FPG will be summarized/analysed only if measured on or prior to the first dose of rescue medication.

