4.3.3.1 Rescue Medication Due to Lack of Glycemic Control in the Treatment Period

Patients with lack of glycemic control during the 24-week treatment period may be eligible to receive open-label rescue medication in addition to their blinded treatment in order to treat ongoing hyperglycemia. Patients may receive open-label rescue medication added on to, but not as a replacement for, their current study drug regimen. Rescue medication in this protocol refers to any approved, appropriate anti-diabetic agent, except SGLT2-inhibitors, for which there is either initiation or upward titration, in accordance with the approved label and

conventional standards of care. Open-label rescue medication is to be titrated as needed to obtain adequate glycemic control. Patients who received a first rescue medication, who subsequently fulfil lack of glycemic control criteria, may have other rescue medications added or substituted, according to Investigator judgment.

During the 24-week double-blind treatment period, all rescue decisions will be based on central laboratory FPG and confirmatory FPG results. If patients meet the protocol-specified glycemic criteria based on FPG, they will be recommended for open-label rescue medication.

Between scheduled visits, the patients will be asked to check their blood glucose if they develop symptoms suggestive of hyperglycemia. The sections and tables listed below define the lack of glycemic control criteria. Glucometers will be provided by AstraZeneca. The patients will receive instructions for the use of the glucometer according to the manufacturer's instructions. Patients will be instructed to contact the investigator if they experience a hyperglycemic event in order to schedule an extra visit for central laboratory FPG and if needed, a confirmatory, repeat FPG.

Patients in the follow-up phase will not need to adhere to the protocol defined rescue criteria, and may have their anti-diabetic regimen adjusted at the Investigator's discretion.

The sections and tables listed below define the lack of glycemic control criteria for initiation of open-label rescue medication.

Protocol-Defined Lack of Glycemic Control Criteria for Initiation of Open-Label Rescue Medication

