Pre-specified glycemic criteria (see [Table 2](#) below), based upon central laboratory FPG and confirmatory, repeat FPG, have been established during the 24-week double-blind treatment period, from Week 4 and up to Week 24 visits, to determine eligibility for open-label rescue medication initiation/titration.

Table 2 **Lack of Glycemic Control Criteria for Initiation of Open-Label Rescue Medication**

Visit Label	Central Laboratory FPG
From Week 4 (Visit 6) to Week 12 (Visit 7) (excluding Week 12)	FPG >240 mg/dL (13.3 mmol/L)
From Week 12 (Visit 7) to Week 24 (Visit 8) (excluding Week 24)	FPG >200 mg/dL (11.1 mmol/L)

Patients with a central laboratory FPG value meeting the lack of glycemic control criterion at a pre-specified visit will be scheduled for a follow-up visit (within 3 - 5 days) to obtain a second central laboratory FPG value and review the patient's glucose meter readings. If the repeat central laboratory FPG value still meets the criterion, the patient will receive rescue medication.

Irrespective of study visit number, patients who meet rescue criteria in the treatment period must first complete the Week 24 visit procedures before receipt of open-label anti-diabetic rescue medication to ensure that important study endpoint measurements are collected.

Following completion of the Week 24 “Rescue” visit, rescued patients will be administered open-label rescue medication in addition to their blinded study drug. Rescued patients will then continue in the treatment period according to their original visit schedule. Patients who received a first open-label anti-diabetic rescue medication, who subsequently fulfill lack of glycemic control criteria described in the [Table 2](#) above, may have other rescue medications added or substituted, according to Investigator judgment, without repetition of rescue visits.

Patients with a central laboratory FPG value >200 mg/dL (11.1 mmol/L) at Week 24 (Visit 8), will not be considered as rescued for efficacy analysis.

Guidelines with regard to changes in insulin dose

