Each patient’s baseline insulin therapy should remain unchanged wherever possible throughout the double-blind treatment period. The stable insulin regimen aims to continue insulin as it was being used by the patient at enrollment and lead-in, with no changes to insulin type and with as few changes in insulin dosage as possible. A stable insulin regimen is pivotal, because it makes it possible for the study to measure any differences in glycemic control between the dapagliflozin treatment arm and the matching placebo arm. Down-titration of insulin will be allowed only as necessary to prevent low blood glucose or hypoglycemia. During the double-blind treatment period, a few patients will experience poor glycemic control, as measured by increased FPG measurements from the central laboratory during study visits. When glucose measurements exceed certain limits (as specified in [Table 2](#) above), the patient will be “rescued”.

During the double-blind treatment period, if up-titration of insulin dose is $>10\%$ (lasting more than 7 consecutive days) in comparison to the mean daily insulin dose at baseline, the patient shall be handled as administration of anti-diabetic rescue medication (i.e., the patient must complete the Week 24 visit procedures, as outlined in section [4.3.5](#)) and the patient will continue in the treatment period according to their original visit schedule. Patients must record the daily dose of insulin in the diary provided (minimum of 80% of days with a value) and review any changes in insulin doses with their investigator, either at regularly scheduled visits, or via telephone calls between visits. Patients required to be rescued, shall be called for an unscheduled visit within 5 days, to complete the Week 24 procedures.

Any insulin dose changes (even if more than $\pm 10\%$ of the mean daily insulin dose at baseline) is not considered as an up or down titration as long the insulin dose change is not for a period of more than 7 consecutive days. For example, dose changes due to known changes in physical activity or food intake will not be registered as up or down titration as long as the insulin dose is back to the previous dose after the change. Similarly, if insulin requirement has increased temporarily, e.g., due to an infection, it will not be considered an up-titration even if the insulin dose increase is more than 10% of the baseline mean daily insulin dose, as

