#### 4.1.7 Handling of Dropouts or Missing Data

The primary estimand will be the treatment difference at Week 24 if all subjects had remained in the trial and received treatment as planned without rescue medication. In order to address the impact of missing data, initiation of rescue therapy, and premature treatment discontinuation on the primary efficacy analysis, the analysis of the primary efficacy endpoint will be repeated in sensitivity analyses.

For the assessment of efficacy, interpretation of results in the presence of missing data depends on the missing data mechanism assumptions as well as on the use of data collected after initiation of rescue therapy or premature study treatment discontinuation in the analysis. In this study, the primary efficacy analysis is performed using an MMRM which assumes MAR, and based on data collected up to initiation of rescue or premature study treatment discontinuation, whichever occurs first.

Two additional methods of sensitivity analyses will be performed. These are Multiple Imputation based on Retrieved Dropouts (MI-RD) and Washout Imputation based on Randomized Set.

In multiple imputation a common (fixed) seed value of 29653, and 1000 simulations will be performed. The detailed analysis plan and implementation of these methods are described in Sections 4.1.7.1 and 4.1.7.2 to, respectively.

To address the impact of missing data on primary efficacy analysis, the amount of missing data, the distribution of missing data among treatment groups, and the reasons for missing data will be examined. The proportion of patients with missing HbA1c assessments will be summarized by treatment group, scheduled time point during the double-blind treatment period, and categories of missing causes if applicable. In addition, spaghetti plots of mean HbA1c profiles over time will be provided for each treatment to assess the patterns of missing HbA1c assessments, with patients grouped according to the time of the last assessment prior to rescue or discontinuation.

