#### 4.2.6 Efficacy Variables

##### 4.2.6.1 Primary Efficacy Variable

The primary objective of this study is to compare the mean change from baseline in HbA1c between dapagliflozin 10 mg and placebo, after 24 weeks of oral administration of double-blind treatment in patients with type 2 diabetes and CKD stage 3A. The primary estimand will be the treatment difference at Week 24 if all patients had remained in the trial and received treatment as planned without rescue medication. The analysis of the primary estimand will include all available data up to Week 24 or premature discontinuation of randomized treatment, whichever occurs first.

The null and alternative hypotheses of interest are:

$$H_0: \mu_s = \mu_p \text{ VS } H_a: \mu_s \neq \mu_p,$$

Where  $\mu_s$  and  $\mu_p$  are mean change from baseline to week 24 in HbA1c for study medication dapagliflozin and placebo groups respectively.

For rescued patients, measurements obtained after rescued medication or rescued insulin will be excluded. For patients discontinuing double-blind medication, measurements obtained after discontinuation will be excluded.

The primary analysis for the change in HbA1c from baseline at Week 24 will be based on longitudinal repeated measures analysis as described in Section 4.1.6.1. For all patients that are administered rescue therapy or discontinue treatment during the double-blind treatment period, only those measurements made on or prior to rescue or treatment discontinuation, (whichever occurs first) the will be included in analysis. For the primary efficacy analysis, the additional 3-way interaction term Baseline\*Week\*Treatment will be used as a model check to assess if there is statistically significant treatment effect across visits which differs in dependency on baseline values.

Point estimates and 95% confidence intervals for the mean change within each treatment group as well as for the differences in mean change between dapagliflozin 10 mg treatment group and the placebo treatment group will be calculated. P-value will be calculated to compare the treatment effect in the dapagliflozin 10 mg treatment group to that in the placebo treatment group.

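### Does an insulin increase that becomes rescue only after 7 days leave SAP 4.3.2 without a workable cut date for HbA1c and FPG?

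*SAP*

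**What the plan says.** Protocol section 4.3.3.1 has two routes to rescue.

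- **FPG route.** A central laboratory FPG above the Table 2 limit is confirmed by a repeat. Below that table the protocol says that patients who meet rescue criteria "must first complete the Week 24 visit procedures before receipt of open-label anti-diabetic rescue medication to ensure that important study endpoint measurements are collected".
- **Insulin route.** An increase of more than 10% over the baseline mean daily dose is handled as rescue if it lasts more than 7 consecutive days. Shorter changes are not counted as titration. Then: "Patients required to be rescued, shall be called for an unscheduled visit within 5 days, to complete the Week 24 procedures". Patients also "review any changes in insulin doses with their investigator, either at regularly scheduled visits, or via telephone calls between visits".

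The same section defines the term: "Rescue medication in this protocol refers to any approved, appropriate anti-diabetic agent, except SGLT2-inhibitors, for which there is either initiation or upward titration".

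The SAP sets the cut in three places. Section 4.1.3 keeps glycemic values up to and including the date rescue is administered. Section 4.2.6.1 says "For rescued patients, measurements obtained after rescued medication or rescued insulin will be excluded". Section 4.3.2 says "The efficacy measurements of HbA1c and FPG will be summarized/analysed only if measured on or prior to the first dose of rescue medication". Section 4.1.7 gives the primary estimand as the Week 24 difference had all patients stayed in the trial and "received treatment as planned without rescue medication".

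**The concern.** The rescue visit is meant to secure a last glycemic value before rescue starts. On the insulin route, rescue status depends on how long the higher dose has already been taken, so the visit normally follows the first rescue dose. Two readings of the cut then seem open. If rescue is dated at the first higher dose, the HbA1c and FPG from the rescue visit are discarded. If it is dated at the visit, values taken on raised insulin enter the primary model as pre-rescue, against the estimand.

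The choice could decide whether a patient's Week 24 value is observed or missing. An increase begun before Visit 6 could leave a patient with no usable post-baseline HbA1c. If placebo patients raised insulin more often, the treatment difference might shrink.

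**Working it through.** **1. The plan's own sample size.** Inputs from Protocol 8.2 and SAP 1.4: SD 0.9, difference 0.3, two-sided 0.05, 80% power.

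- n per group = 2 × (1.960 + 0.842)² × (0.9/0.3)² = 2 × 7.85 × 9 = 141.3, so 142 by the normal approximation. The t-test gives 142.2, rounded up to the stated 143.
- 143/0.95 = 150.5, rounded up to 151 per group, 302 in all.
- SE = 0.9 × √(2/143) = 0.1064. Power = Φ(0.30/0.1064 − 1.96) = 0.80.

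The figures reproduce, and nothing below alters them.

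**2. Timing on the insulin route.** Let u be the first day at the higher dose. More than 7 consecutive days is first true on day u+7. A visit within 5 days falls on u+7 to u+12, a lag of 7 to 12 days. The extreme case starts the day after Visit 7 (day 86) and is found only at Visit 8 (day 169): 169 − 86 = 83 days. That needs no telephone review in between, although the protocol provides for calls.

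**3. Candidate rescue dates against the text.**

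| Rescue dated at | Rescue-visit days kept by the cut | Support in the documents |
|---|---|---|
| First higher dose, day u | 0 of 6 | First rescue dose (SAP 4.3.2), date of administration (4.1.3), rescued insulin (4.2.6.1), with upward titration being rescue medication (Protocol 4.3.3.1) |
| Day the condition is met, u+7 | 1 of 6 | Possible, not stated |
| Rescue visit | 6 of 6 | None |

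The first two readings agree on 5 of the 6 possible visit days. Only the unsupported third keeps the visit value as a rule.

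**4. How many patients the date could touch.** Neither the insulin share nor the up-titration rate is given. Assume 25% to 65% on insulin and 5% to 15% of placebo insulin patients up-titrating; the simulation below then yields 2.7 to 22 events among 286 patients. Possible start days run from 2 to 168, which is 167 days.

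- *Week 24 observed or missing.* The Week 24 window opens on day 128 (SAP Table 17). A visit on u+7 within days 128 to 169 needs u = 121 to 162: 42/167 = 25.1%.
- *No post-baseline HbA1c under first-dose dating.* HbA1c is first drawn at Visit 6, day 29, so u = 2 to 28: 27/167 = 16.2%.

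These are shares of calendar days, not probabilities. If start days were uniform, they would mean 0.7 to 5.5 patients (0.2515 × 2.7 and × 22) and 0.4 to 3.6 patients (0.162 × 2.7 and × 22). The 5% allowance for patients without usable HbA1c is 302 − 286 = 16.

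**5. Effect on the estimate.** Simulation with 143 per arm, SD 0.9 and a Week 24 effect of −0.30. All other inputs are assumed: visits at Weeks 4, 12 and 24; effects −0.15 and −0.28 at the first two; between-visit correlations 0.70, 0.75 and 0.55; start day uniform on 86 to 161; HbA1c fall on higher insulin of 0.3 or 0.8 over 84 days; recognition on days 8 to 13 or at Visit 8.

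| Trigger for up-titration | Bias, first-dose date | Bias, visit date |
|---|---|---|
| Unobserved Week 24 change above the placebo 95th or 85th centile | +0.005 to +0.029 | +0.001 to +0.026 |
| Observed Week 12 value | −0.001 to +0.001 | 0.000 to 0.017 |

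With the first trigger, a separate build of eight scenarios (1,500 runs) put the gap between the two dates at 0.002 to 0.021, first-dose bias being the larger in all eight.

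At the largest first-dose bias, power = Φ(0.271/0.1064 − 1.96) = 0.72; at the smallest, Φ(0.295/0.1064 − 1.96) = 0.79. That loss belongs to the first-dose date, under a trigger that violates missing-at-random by construction. When the trigger depends on observed data, the first-dose bias vanishes. The loss therefore measures an assumed failure of MAR, which any pre-rescue MMRM shares, and not the missing definition.

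**The case for a change.** The best case for a change is that neither document names the day, so two programmers could build different primary datasets. SAP section 1.2 describes only the FPG route. SAP section 4.3.10 adds to the doubt by testing for an increase of at least 10% on interpolated doses with no duration, whereas the protocol has more than 10% for more than 7 consecutive days. MI-RD and washout imputation use data regardless of rescue, so they address another estimand and do not test the date. One sentence in the SAP would be cheap.

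Part of this stands. The date is not stated in words. The wording of SAP 4.3.10 and Protocol 4.3.3.1 differs and must be reconciled by the sponsor; no clinical rule is proposed here. That difference concerns which patients count as rescued, not where the cut falls once they do. Protocol 5.1.8 has the investigator calculate a mean dose since the last visit, so the start day may have to come from the diary or from the dated dose records that SAP 4.3.10 describes. The two imputation analyses are indeed no test of the date, although neither depends on it.

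The charge that no rescue date can satisfy every passage goes too far. The visit-first sentence follows the FPG criteria, and the insulin paragraph sets out its own steps. Where a lasting increase is agreed with the investigator beforehand, the visit can still come first. Whether the sentence was meant to cover the insulin route is for the sponsor to reconcile, but the analysis cut is the same either way.

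**Conclusion.** No change to the plan follows. This is a missing detail that an analyst fills correctly by reading the SAP as written. Three SAP sections and the protocol's definition of rescue medication lead to the first higher dose, and that gives a pre-rescue analysis consistent with the estimand. Losing the insulin rescue-visit value is a real cost, since the aim of collecting endpoints before rescue is normally missed on this route. But a value taken after a week or more on raised insulin is not one this estimand wants, and earlier HbA1c values stay in the MMRM. SAP 4.1.3 does not cut body weight and seated SBP at rescue.

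The size is small as far as it can be judged: about 3 to 22 patients of 286, and a shift between the two dates of 0.002 to 0.021 points against 0.30, at most 0.021/0.1064 = 0.20 of a standard error. Both ranges rest on assumed insulin use, up-titration rates, triggers and start days. Writing the first-dose date into the SAP would not alter an analysis that already follows it and would recover none of the simulated power loss. An added sensitivity run or a table of insulin-route rescues would be a matter of preference.

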#### 4.3.3 Assignment of Dates to Adverse Events and Laboratory Assessments

In case of missing dates and/or times, imputation rules will be applied as follows:

For AEs, a missing or incomplete onset date will be imputed according to the following conventions:

1. If the onset date for an AE is missing or incomplete, an imputed date will be derived to slot the event to an appropriate analysis period. This derived date will not be reported in summary tables or listings.

Exception: No dates will be imputed for SAEs. Every effort will be made to determine the actual onset date for the event or to obtain a reliable estimate for the onset date from the investigator.

2. If an onset date is missing, the derived onset date will be calculated as the first non-missing valid date from the following list (in order of precedence):
  - First active study medication date
  - Consent date
  - Visit date corresponding to the visit at which the event was reported.
  - If a valid non-missing date is not available for any of these dates, the derived onset date will be set to missing.
3. If an onset date is incomplete, the derived onset date will be calculated using the following algorithm:
  - Calculate a surrogate date as the first non-missing valid date from the following list (in order of precedence):
    - First active study medication date
    - Consent date
    - Visit date corresponding to the visit at which the event was reported
    - If a valid non-missing date is not available for any of these dates, the surrogate date will be set to missing.
  - Based on the information provided, set the derived date to the earliest possible date. If only a year is provided, set the derived date to January first of that year. If a year and month is provided, set the derived date to the first day of that month.
  - If the surrogate date is non-missing then:
    - If the derived date is on or after the surrogate date use the derived date as calculated
    - If the derived date is before the surrogate date and the surrogate date is consistent with the partial data provided for the onset date, use the surrogate date as the derived date
    - If the derived date is before the surrogate date and the surrogate date is not consistent with the partial data provided for the onset date then set the derived onset date to be the latest possible date based on the partial onset date information provided. If only a year is provided, set the derived date to December 31st of that year. If a year and month is provided, set the derived date to the last day of that month.

- If all three dates used to determine the surrogate date are missing, then based on the information provided, set the derived date to the earliest possible date. If only a year is provided, set the derived date to January first of that year. If a year and month is provided, set the derived date to the first day of that month.

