3.3 Patient enrolment and randomization

Investigator(s) should keep a record, the patient screening log, of patient who entered pre-study screening.

The Investigator(s) will:

1. Obtain signed informed consent from the potential patient before any study specific procedures are performed. Patient is considered enrolled in the study after she/he has signed the informed consent form (ICF).

CCI

3. Determine patient eligibility. See Section 3.1 and 3.2
4. Assign eligible patient unique randomization code, by accessing IVRS or IWRS, see Section 3.5. Patient is considered randomized in the study after this assignment.

Patients entering the single-blind placebo lead-in period

At the time of entry into the single-blind placebo lead-in period, the site will contact the IVRS/IWRS in order that lead-in medication can be assigned and dispensed.

Patient who does not meet the eligibility criteria is considered as screen failure in the study. These patients will be terminated from the study and registered as Screen Failure by using IVRS/IWRS. See section 3.10.1.

Patients entering the double-blind treatment period

Following completion of the single-blind lead-in period, patients eligible for double-blind treatment will be randomly assigned to one of the two treatment arms by the IVRS/IWRS in a 1:1 ratio (dapagliflozin 10 mg: matching placebo) using a randomization schedule.

If a patient discontinues/withdraws from the study, then his/her enrolment/randomization code cannot be reused.

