6.3 Recording of adverse events

6.3.1 Time period for collection of adverse events

AEs will be collected from the start of the placebo lead-in period throughout the treatment period (Visit 2 to 8) and including the follow-up period (Visit 9).

SAEs will be recorded from the time of informed consent is obtained until the end of the study (Visit 9).

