#### **4.2.7 Safety Variables**

The Safety Analysis Set will be used for all safety analyses, including all data after rescue during the double-blind treatment period. Sensitivity analyses on data collected prior to rescue during the double-blind treatment period will be performed for selected Adverse Events (AEs) as described in multiple sub-sections under Section 4.2.7.1.

Safety analyses will be conducted on the double-blind treatment period and follow-up period.

AEs within 4 days or SAEs within 30 days post last double-blind study medication, which are considered in the double-blind treatment period, will not be counted as AEs or SAEs during the follow-up period.

Unless otherwise specified, the safety analyses of changes from baseline to a specific time point in safety variables (e.g., laboratory parameters and vital signs) will only include patients from the Safety Analysis Set who have data available for both the baseline and the time point under consideration.

Safety data that collected before randomization will not contribute to summaries but will be listed.

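### The AE onset-date rule in SAP 4.3.3 never uses the reporting visit, so a non-serious lead-in event whose onset date is missing, or partial but compatible with first dose, can be given a Day 1 onset after it was reported

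*SAP*

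**What the plan says.** SAP 4.3.3 gives the purpose of the imputation: "an imputed date will be derived to slot the event to an appropriate analysis period". For a non-serious event with no onset date, "If an onset date is missing, the derived onset date will be calculated as the first non-missing valid date from the following list". The list is, in order:

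1. "First active study medication date"
2. the consent date
3. "Visit date corresponding to the visit at which the event was reported"

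For a partial date the same list supplies a surrogate date, and there are three branches:

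- If the earliest date that the partial data allow is on or after the surrogate, that earliest date is used.
- "If the derived date is before the surrogate date and the surrogate date is consistent with the partial data provided for the onset date", the surrogate is used.
- If the earliest date is before the surrogate and the surrogate does not fit the partial data, the latest date that the partial data allow is used.

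SAE dates are not imputed; the site is to supply the actual date or a reliable estimate.

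Three other rules bear on this. Protocol 6.3.1: "AEs will be collected from the start of the placebo lead-in period throughout the treatment period", so lead-in events are in the database. SAP 4.2.7.1.1 summarizes events with onset in the double-blind period. SAP 4.2.7: "Safety data that collected before randomization will not contribute to summaries but will be listed".

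**The concern.** The only entry in the list that carries information about the event itself is the reporting visit, and it stands last, behind two dates that a treated patient always has. The rule can therefore place the onset of an event after the visit at which the site recorded it. When that visit fell in the placebo lead-in, an event known to precede double-blind treatment is given an on-treatment date.

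What is at stake is the content of the double-blind AE tables, and an unresolved disagreement between two SAP rules. One selects events by derived onset. The other excludes data collected before randomization. For the same event they give different answers, and the SAP does not say which prevails.

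**Working it through.** The documents state no figure on this point, so there is none to reproduce. The check is to follow the rule as written.

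**Inputs**

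- Day 1 is the day of the first double-blind dose (SAP 4.1).
- Visit 3 is at Day -7 and Visit 4 at Day 1 (Protocol Table 1). At Visit 4 the first dose follows the visit procedures on the same date (Protocol 3.5).
- The lead-in lasts 4 weeks, or 28 days (Protocol 7.2).
- Consent is universal among enrolled patients: "Obtain signed informed consent from the potential patient before any study specific procedures are performed" (Protocol 3.3).
- AE stop dates are collected (Protocol 6.3.3), but the onset rule does not use them.

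**Worked case.** First dose 14 March 2016, event reported at Visit 3 on 7 March:

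| Onset as recorded | Branch | Derived onset |
|---|---|---|
| Missing | first date in list | 14 March 2016 (Day 1) |
| March 2016 | surrogate fits | 14 March 2016 (Day 1) |
| 2016 only | surrogate fits | 14 March 2016 (Day 1) |
| February 2016 | surrogate does not fit | 29 February 2016 (pre-treatment) |
| 2015 only | surrogate does not fit | 31 December 2015 (pre-treatment) |

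The first three rows put onset seven days after the event was reported. The last two are correct.

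**All lead-in onsets.** The rule was run for each first-dose date from 1 August 2015 to 31 July 2017 (731 dates) and each of the 28 preceding days: 731 x 28 = 20,468 combinations, under three kinds of missingness, or 61,404 runs. Assumptions: dates uniform, consent 42 days before first dose, and the first list entry read as the first double-blind dose.

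- Reporting-visit date used: 0 of 61,404 runs.
- Lead-in onsets moved to Day 1: wholly missing 100%; year only 96%; year and month 52%.
- The remaining 4% and 48% stay before treatment.

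**Size.** The documents give neither an AE rate nor a missing-date rate. Assume 1 to 2 AEs per patient over 24 weeks and 2% to 5% with incomplete dates:

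- Lead-in AEs: 302 x 1 x 4/24 = 50, to 302 x 2 x 4/24 = 101.
- With incomplete dates: 50 x 0.02 = 1, to 101 x 0.05 = 5.

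This counts every incomplete date as moved, so it is an upper range for those rates. If year and month were always known, 52% would move: about 0.5 to 2.6 events.

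**What a cap at the reporting visit leaves.** Lead-in onsets in the last 6 of the 28 days are first reported at Visit 4, which has the same calendar date as the first dose. For wholly missing onsets, 6/28 = 21% would still fall on Day 1, so a cap alone is not enough.

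**The case against.** Four arguments limit the point.

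*SAP 4.2.7 may already cover it.* That rule turns on when data were collected, not on derived onset. An event reported at Visit 3 was collected before randomization and could be kept out of the summaries on that ground. This is a fair reading, but the AE section selects by onset and sends missing dates to SAP 4.3.3, with no statement of precedence. A clarifying line is still needed.

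*Placing uncertain onsets at treatment start is a cautious convention.* True where the timing is unknown. It also explains why an undated event first reported at Visit 9 goes to Day 1, which the fix below leaves alone. It does not justify the date where the reporting visit shows that the event came before dosing.

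*It affects both arms alike.* With the first double-blind dose as the anchor, the rule is the same in each arm. Safety results are descriptive, without inferential testing (Protocol 8.5.7, SAP 3.4), and a patient counts once per preferred term (SAP 4.3.8). This stands and keeps the point minor.

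*Partial dates are largely handled.* This stands as well. A reader might infer that every incomplete lead-in date becomes Day 1, but the third branch keeps an event pre-treatment when its known month or year precedes first dose.

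Two stronger readings are tempting. The word 'active' in the first list entry might suggest that placebo patients have no such date, so that their undated events fall to the consent date and leave the tables while dapagliflozin events stay. SAP 4.1.7.2 does use the word for dapagliflozin as against placebo. But SAP 4.1 defines Day 1 by double-blind medication, SAP 4.2.5.1 starts study therapy at the first investigative or comparator dose, and the word can simply separate double-blind drug from lead-in placebo. This is an ambiguity, not evidence of bias between arms.

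A reader might also infer that undated SAEs are dropped. No rule says so. SAP 4.3.3 requires every effort to obtain a date or an investigator's estimate, and SAP 4.2.7.1.3 lists all SAEs. What remains is an SAE whose date is never recovered, for which the plan gives no tabulation rule.

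**Conclusion.** The point holds for non-serious events whose onset date is wholly missing, or partial and compatible with the first-dose date. For these the reporting visit is never consulted, and a lead-in event can receive an onset later than its own report. That meets the double-blind onset definition and conflicts with the SAP's exclusion of data collected before randomization, unless that exclusion is meant to override.

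The conclusion on the rule needs no assumption beyond reading the first list entry as the first double-blind dose. The size does rest on assumptions: a few events at most in 302 patients at the assumed rates. No test, error rate or efficacy result is touched. This is a low-priority correction.

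**What to change.** In SAP 4.3.3:

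1. State that the derived onset may not be later than the visit at which the event was first reported, or than the recorded AE stop date.
2. State that AEs reported at or before Visit 4, prior to the first double-blind dose, are pre-treatment and stay out of the double-blind summaries under SAP 4.2.7. This deals with the shared calendar date at Visit 4.
3. As a wording clarification, replace "First active study medication date" with *first double-blind dose date (either arm)*.

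Optionally, add a line on how an SAE still undated at clean file is tabulated.

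The cost is a few short SAP edits and some lines in the AE derivation program, using data already collected. They should be made before unblinding.
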